### **8.4.4 Vital Signs**

Summaries of vital sign values will be provided separately for Parts A and B based on the Safety Set.

For the vital sign measurements during the TE period for the Safety Set for the corresponding part, the observed values and change from baseline values will be summarized at each visit separately for Parts A and B. The following vital signs parameters will be summarized: BMI ( $\text{kg}/\text{m}^2$ ), weight (kg), systolic and diastolic blood pressure (mm Hg), body temperature ( $^{\circ}\text{C}$ ), pulse rate (beats per minute), and respiratory rate (breaths per minute).

The number and percentage of subjects meeting at least 1 threshold analysis criterion during the TE period for the corresponding part will be summarized separately for Parts A and B. The threshold analysis criteria are provided in [Appendix D](#).

In addition, a listing containing individual subject vital sign values will be provided separately for Parts A and B. This listing will include data from both scheduled and unscheduled visits.

### **8.4.5 Pulse Oximetry**

Summaries of pulse oximetry values will be provided separately for Parts A and B based on the Safety Set.

For the percent of oxygen saturation measurements using pulse oximetry during the TE period for the Safety Set for the corresponding part, a summary of observed values and change from baseline values will be provided at each visit separately for Parts A and B.

The number and percentage of subjects with shift changes from baseline (normal/missing and low according to the reference range) to the lowest percent of oxygen saturation during the TE Period for the corresponding part will be summarized separately for Parts A and B. The reference range for normal oxygen saturation is specified as  $>95\%$ , and  $\leq 95\%$  for low oxygen saturation.

### **8.4.6 Physical Examination**

No tables/figures/listings will be provided for PE data.

### **8.4.7 Ophthalmology Examination**

[figure not shown]
Ophthalmology examination results will be provided in a data listing separately for Parts A and B, as applicable.

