#### **11.4.7 Ophthalmologic Examination**

Ophthalmologic examinations will be conducted only for subjects who were <18 years of age on the date of informed consent in the parent studies of Study 659-105. The examination does not need to be completed if there is documentation of bilateral lens removal for the subject.

All examinations will be conducted by a licensed ophthalmologist or optometrist and will include

- measurement of best-corrected distance visual acuity of each eye; and
- pharmacologically dilated examination of the lens with a slit lamp.

Subjects <18 years of age on the date of informed consent in the parent studies of Study 659-105 are required to complete a total of 2 ophthalmologic examinations as indicated in [Table 3-1](#). These examinations should be completed within 28 days of the relevant study visit. A single ophthalmologic examination is required at completion of study participation (defined in [Section 9.1.5](#)) except for subjects who have withdrawn consent or assent. Ophthalmologic examinations are only required if the cumulative drug exposure (in Study 659-105 and current study) is at least 12 weeks since the last study ophthalmologic examination.

Any clinically significant abnormal findings will be reported as AEs.

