## 6.2 Sample Size and Power

The primary objective of the study is the evaluation of the long-term safety and tolerability of ELX/TEZ/IVA. This is an open-label study that enrolled subjects previously enrolled in Study 659-105 and met the Study 445-113 eligibility criteria.

Over 400 subjects were enrolled. With this number of subjects exposed to ELX/TEZ/IVA treatment, AEs by Preferred Term (PT) that occur with a frequency of >1% will be ruled out with 95% confidence, when 0 events are observed in that PT.

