## **7 ANALYSIS SETS**

The following analysis sets are defined: All Subjects Set and Safety Set.

The **All Subjects Set** for Parts A and B are defined as all subjects who were enrolled (defined as subject having data in the clinical database) in Part A or Part B of this study, respectively. This analysis set will be used for individual subject data listings and disposition summary tables unless otherwise specified.

The **Safety Sets** for Part A and B are defined as all subjects who have received at least 1 dose of study drug in Part A or Part B of this study, respectively. The Safety Set will be used for all safety analyses unless otherwise specified.

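### Lens findings are looked for only in the under-18 group but summarised over the whole Safety Set, which dilutes them and leaves examination-detected findings outside the SAP 6.2 rule-out unless at least 299 subjects are examined

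*SAP*

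**What the plan says.** **Who is examined.** Protocol 11.4.7 states: "Ophthalmologic examinations will be conducted only for subjects who were <18 years of age on the date of informed consent in the parent studies"; these are the two studies that fed Study 659-105. Besides visual acuity, the examination includes a "pharmacologically dilated examination of the lens with a slit lamp". Protocol Table 3-1 ties it to Week 48, Week 96 and, for early discontinuation, the ETT Visit; none is scheduled at Day 1. Subjects with documented bilateral lens removal are exempt. An examination is required only after 12 weeks or more of exposure, counted across Study 659-105 and this study, since the last one. The synopsis admits subjects from 12 years with no upper age limit, and no document gives the number under 18.

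**How findings are reported.** Under Protocol 11.4.7, findings judged clinically significant become AEs. For the examination itself, SAP 8.4.7 says: "Ophthalmology examination results will be provided in a data listing separately for Parts A and B, as applicable". Ophthalmology is not among the endpoints listed for summary in SAP 8.4, and the events of special interest in SAP Appendix E are elevated transaminases and rash. The TEAE tables in SAP 8.4.1 give the number and percentage of subjects and the exposure-adjusted rate by PT, for each part. On the denominator, SAP 7 says: "The Safety Set will be used for all safety analyses unless otherwise specified".

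**The precision statement.** SAP 6.2 says "Over 400 subjects were enrolled" and then: "AEs by Preferred Term (PT) that occur with a frequency of >1% will be ruled out with 95% confidence, when 0 events are observed" for a given PT. It does not distinguish PTs by how the events are found.

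**The concern.** A percentage is interpretable when everyone in the denominator had a comparable chance of entering the numerator. Here the under-18 group has its lenses examined by slit lamp, while adults are in the denominator without any scheduled examination that would show an opacity causing no symptoms. The TEAE tables pool the two groups, and lens findings not judged clinically significant reach no readable table.

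What is at stake is the reading of a safety result in minors. The protocol gives this group its own scheduled examination, but the planned tables cannot answer the obvious question: what proportion of examined subjects had a lens finding? If no lens PT is reported, a reader applying SAP 6.2 would conclude that the frequency is below 1%, although for symptomless findings only the examined subjects supply information.

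**Working it through.** **Inputs.** Total 400 subjects, 0 events, 1% and 95% confidence, all from SAP 6.2. The examined share *s* is not in the documents; I **assume** 15%, 25% or 35%, that is 60, 100 or 140 of 400.

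**1. Reproduce the plan's figure.** With 0 events in n subjects, the exact one-sided 95% upper bound is 1 − 0.05^(1/n).
- n = 400: 1 − 0.05^(1/400) = 0.75%. The SAP statement is reproduced. The two-sided bound, 1 − 0.025^(1/400) = 0.92%, is also below 1%.
- Smallest n that rules out 1%: ln 0.05 / ln 0.99 = 298.1, so 299 subjects, or 299/400 = about 75% of the total (368 subjects with the two-sided bound).

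**2. Dilution of the percentage.** If every lens event arises in examined subjects, the Safety Set percentage is *s* times the percentage in the examined group, so the dilution is 1/*s*. The exposure-adjusted rate is diluted by the same factor if mean exposure is alike in both groups.

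**3. Bound for the examined group.** Use the step 1 formula with n examined subjects. The chance of seeing no event at a true frequency of 1% is 0.99^n.

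| Assumed share | n examined | Dilution 400/n | 3 findings over 400 | 3 findings over n | Upper bound, 0 findings | P(0 findings) at true 1% |
|---|---|---|---|---|---|---|
| 15% | 60 | 6.7 | 0.75% | 5.0% | 4.9% | 0.55 |
| 25% | 100 | 4.0 | 0.75% | 3.0% | 3.0% | 0.37 |
| 35% | 140 | 2.9 | 0.75% | 2.1% | 2.1% | 0.24 |

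Even with half of the subjects examined (n = 200) the bound is 1.5%. The 12-week exposure condition and the lens-removal exemption can only lower the number who must be examined.

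**4. Allow for lens AEs in adults.** If unexamined subjects yield a fraction *f* of the detected rate in examined subjects, the dilution is 1/(*s* + (1 − *s*)*f*). Both values of *f* are illustrations.
- *f* = 0.10: 1/(0.15 + 0.085) = 4.3; 1/(0.25 + 0.075) = 3.1; 1/(0.35 + 0.065) = 2.4.
- *f* = 0.25: 1/(0.15 + 0.2125) = 2.8; 1/(0.25 + 0.1875) = 2.3; 1/(0.35 + 0.1625) = 2.0.

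So 1/*s* is a ceiling. The direction of the effect does not change.

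**The case against.** **The size is assumed.** A reader might infer that the lens percentage is known to be diluted about 3- to 7-fold. The documents do not support that: the figure is the reciprocal of a chosen share, and it also requires that no adult reports a lens event. All subjects are asked about AEs at every visit (Protocol 13.1.1.3) and the complete physical examination includes the eyes (Protocol 11.4.3), so a symptomatic cataract in an adult can be recorded. This objection stands. It limits the size, not the mismatch.

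**SAP 6.2 is not wrong.** A reader might also infer that the rule-out is miscalculated. It is not: it is correct for AEs ascertained in all exposed subjects. The gap lies in ascertainment.

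**Unreadable text.** Section numbering jumps from 8.4.8 to 8.6, and an item in SAP 8.4.7 is not shown. SAP Appendix E also refers to an analysis of events of special interest that no readable section describes. That lens findings are tabulated only as TEAEs can be asserted for the readable text alone.

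**A matter of presentation.** Ophthalmology is outside the primary endpoint, the analysis is descriptive, and a listing lets a reader count by hand. This is true, but a listing supplies no planned denominator, percentage or bound, and SAP 6.2 makes an explicit confidence statement. For home-collected sweat chloride, SAP 8.6.1 does restrict its summary to subjects with valid values.

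**A simple count would mislead.** With no Day 1 examination and subjects arriving from Study 659-105 (Protocol 8.1), counting every opacity seen after the first dose would mix old findings with new ones. This stands and shapes the fix.

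**Conclusion.** The concern holds for the readable text. Examination-detected lens findings are set against a denominator that includes subjects who were never examined, so the planned percentage understates their frequency. The dilution is at most 1/(examined share): 6.7- to 2.9-fold if 15% to 35% of 400 were examined, and less if adults report symptomatic lens events. Extending this to the exposure-adjusted rate assumes similar mean exposure in both groups.

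The conclusion on the rule-out does not need a precise share. For symptomless, examination-detected findings, 1% is not excluded by zero events unless at least 299 subjects are examined. The point should be corrected, because the result in minors would otherwise look more reassuring than the data allow. It does not touch the primary endpoint or any decision rule.

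**What to change.** **SAP 8.4.7.** Keep the listing and add one small table, per part as applicable (the Part B schedule is not in the supplied protocol):
- denominator: subjects with at least 1 ophthalmologic examination after the first dose in that part;
- n (%) with a lens finding that is new or worse than at the last available earlier study examination;
- separately, findings already present and findings of unknown prior status;
- the exact 95% upper bound for the new or worsened findings, stating whether it is one- or two-sided;
- percentage and exposure-adjusted rate of lens-PT TEAEs in this group, using this group's own exposure.

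**SAP 6.2.** Add that the 1% statement applies to AEs ascertained in all subjects, and not to findings detectable only by the ophthalmologic examination.

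**Cost.** SAP wording and one extra table, with no new visits or examinations. Earlier examination results may have to be brought over from Study 659-105; where they are not available, the finding goes in the unknown row. The stated bound for lens findings becomes less favourable.

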### 8.4.8 Spirometry

Summaries of spirometry will be provided separately for Parts A and B based on the Safety Set.

Summary statistics for raw values of the following spirometry measurements i.e. FEV1 (L), percent predicted FEV1 (percentage points), FVC (L), percent predicted FVC (percentage points), FEF25-75% (L/sec), percent predicted FEF25-75% (percentage points), FEV1/FVC, percent predicted FEV1/FVC (percentage points), will be presented at each visit for Part A and Part B separately.

Percent predicted FEV1 (ppFEV1): the ppFEV1 value is the ratio of FEV1 (L) and predicted FEV1 (L), expressed as a percentage. See [Appendix F](#) for more details.

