#### **12.3.3.7 Spirometry**

Spirometry data (including ppFEV1, FEV1, FVC, FVC/FEV1 ratio, and FEF25%-75%) will be summarized using descriptive statistics.

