### **5 STUDY ENDPOINTS**

#### **5.1 Primary Endpoint**

Safety and tolerability of long-term treatment with ELX/TEZ/IVA based on adverse events (AEs), clinical laboratory values, ECGs, vital signs, pulse oximetry, and spirometry.

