## **8 STATISTICAL ANALYSIS**

### **8.1 General Considerations**

In general, data will be summarized by the treatment group in this study.

The precision standards for reporting safety variables are provided in an internal Biometrics document that specifies the programming rules including the precision for derived variables.

**Continuous variables** will be summarized using the following descriptive summary statistics: the number of subjects (n), mean, standard deviation (SD), median, minimum value (min), and maximum value (max).

**Categorical variables** will be summarized using counts and percentages. Percentages will be presented to 1 decimal place.

**Baseline value**, unless otherwise specified, for the long-term safety analysis is defined as the most recent non-missing measurement (scheduled or unscheduled) collected before the first dose of ELX/TEZ/IVA in Part A of this study.

Baseline of sweat chloride is defined as the most recent non-missing sweat chloride (scheduled or unscheduled) collected before the first dose of VX-659 in VX17-659-102 or VX17-659-103 studies.

**Absolute change** from baseline will be calculated as post-baseline value - baseline value.

**Relative change** from baseline will be calculated as  $100\% \times (\text{post-baseline value} - \text{baseline value}) / \text{baseline value}$ .

**Treatment-emergent (TE) Period** for Part A will include the time from the first dose of study drug in Part A to 28 days after the last dose date of the study drug in Part A or to the completion date of study participation in Part A (Section 9.1.5 of the CSP), whichever occurs first.

**Treatment-emergent (TE) Period** for Part B will include the time from the first dose of study drug in Part B to 28 days after the last dose date of the study drug in Part B or to the completion date of study participation in Part B (Section 9.1.5 of the CSP), whichever occurs first.

The completion date of study participation will be obtained from the end of study page of the eCRF for each part respectively.

For subjects who participate in another qualified Vertex study before completing Study VX18-445-113 and resume participation in Study VX18-445-113, the TE Period for either Part A or B will exclude the time spent in the other study.

**Unscheduled visits:** Unscheduled visit measurements will be included in analysis as follows:

- 1) In scheduled visit windows per specified visit windowing rules

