#### **8.4.2 Clinical Laboratory Assessments**

Summaries of laboratory values will be provided separately for Parts A and B based on the Safety Set.

For the treatment-emergent laboratory assessments, the observed values and change from baseline values of the continuous hematology, coagulation and chemistry results will be summarized in SI units at each visit during the TE period of the corresponding part separately for Parts A and B.

The number and percentage of subjects with selected test values meeting at least 1 threshold analysis criterion event during the TE period of the corresponding part will be summarized separately for Parts A and B. The threshold analysis criterion shift from baseline will also be summarized for selected laboratory test values separately for Parts A and B. The threshold analysis criteria are provided in [Appendix D](#).

For selected LFT laboratory test (alanine transaminase [ALT], aspartate transaminase [AST], alkaline phosphatase [ALP], and total bilirubin), a scatter plot of the maximum treatment-emergent value versus the baseline value corresponding to  $\times$ ULN (upper limit of normal) will be presented for the each part. Furthermore, a scatter plot of the maximum treatment-emergent value of ALT and AST, separately, versus the maximum treatment-emergent value of total bilirubin corresponding to  $\times$ ULN will also be presented for the each part.

Results of positive urine/serum pregnancy test will be listed in individual subject data listings only separately for Parts A and B. For positive serum pregnancy listing, subjects with serum HCG which are abnormally high will be selected separately for Parts A and B.

In addition, a listing containing individual subject hematology, chemistry, coagulation and urinalysis values will be provided separately for Parts A and B. This listing will include data from both scheduled and unscheduled visits.

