### **8.4.3 Electrocardiogram**

Summaries of ECG values will be provided separately for Parts A and B based on the Safety Set.

For the following ECG interval measurements during the TE period of the corresponding part, a summary of observed values and change from baseline values (in msec) will be provided at each visit separately for Parts A and B: RR interval, PR interval, QT interval, and QT corrected for HR (QTcF), QRS duration, and HR (beats per minute).

The number and percentage of subjects meeting at least 1 threshold analysis criterion during the TE period of the corresponding part will be summarized separately for Parts A and B. The threshold analysis criteria are provided in [Appendix D](#).

In addition, a listing containing individual subject ECG values will be provided separately for Parts A and B. This listing will include data from both scheduled and unscheduled visits.

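### Spirometry, part of the primary endpoint, is summarised only as raw values by visit in the visible SAP; the other continuous components also get change from baseline

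*SAP*

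**What the plan says.** SAP 5.1 bases the primary endpoint on adverse events together with "clinical laboratory values, ECGs, vital signs, pulse oximetry, and spirometry".

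The SAP then treats the continuous components as follows:

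- Laboratory (8.4.2): "the observed values and change from baseline values of the continuous hematology, coagulation and chemistry results will be summarized in SI units", at each visit.
- ECG (8.4.3): "a summary of observed values and change from baseline values (in msec) will be provided at each visit".
- Vital signs (8.4.4): "the observed values and change from baseline values will be summarized at each visit separately for Parts A and B".
- Pulse oximetry (8.4.5): "a summary of observed values and change from baseline values will be provided at each visit separately for Parts A and B".
- Spirometry (8.4.8): "Summary statistics for raw values of the following spirometry measurements", at each visit, for Parts A and B separately. Raw here means not expressed as a change, because percent predicted values are on the list.

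SAP 8.1 defines baseline for the whole safety analysis as the last value before the first Part A dose, and says that absolute change "from baseline will be calculated as post-baseline value - baseline value". Table 11-1 gives spirometry a baseline row. Protocol 12.3.3.7 says of spirometry only that it "will be summarized using descriptive statistics".

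**The concern.** Visit-by-visit means of raw values follow whoever was measured at each visit. Protocol 9.9 allows subjects to stop study drug when they become eligible for the commercial product, and SAP 8.2.1 counts departures to another study. Protocol 9.10 says that withdrawn subjects are not replaced, and SAP 8.1 that missing data are not imputed unless specified. A rise or fall in mean percent predicted FEV1 (ppFEV1) across Part A could therefore reflect change within subjects, a change in who remains, or both.

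There is a second loss even if nobody leaves. Raw summaries then give the mean change but not its spread or extremes. The lowest raw value at a visit does not show the largest individual decline, which matters for a safety endpoint in a disease where, as Protocol 5.1 says, progressive loss of lung function is the leading cause of death.

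**Working it through.** The plan gives no figure for spirometry to reproduce. Its one sample-size statement (SAP 6.2) concerns adverse event frequency and does not bear on this point.

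**1. Side-by-side reading of the visible SAP**

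| Component | Observed values by visit | Change from baseline | Threshold or shift analysis |
|---|---|---|---|
| Continuous laboratory values (8.4.2) | yes | yes | yes |
| ECG (8.4.3) | yes | yes | yes |
| Vital signs (8.4.4) | yes | yes | yes |
| Pulse oximetry (8.4.5) | yes | yes | yes (shift) |
| Spirometry (8.4.8) | yes | no | no |

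Urinalysis is only listed, so the comparison is with continuous hematology, coagulation and chemistry. Appendix D has no spirometry criteria. Clinic sweat chloride, which is outside the primary endpoint, also gets change from its own baseline (8.6.1).

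Two other places could be thought to fill the gap, and neither does. The definitions in SAP 8.1 give a formula but assign no output to spirometry. The mention there of maximum and minimum change is a rule on using unscheduled visits.

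**2. Scope**

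- Measures in 8.4.8: FEV1, FVC, FEF25-75% and FEV1/FVC, each also as percent predicted: 4 x 2 = 8.
- On-treatment spirometry visits in Table 11-1: Part A has Day 15 and Weeks 4, 8, 16, 24, 36, 48, 60, 72, 84 and 96 = 11. Part B has Weeks 12, 24, 36 and 48 = 4. Safety Follow-up is not counted.
- Summaries: 8 x 11 = 88 in Part A and 8 x 4 = 32 in Part B, together 120. None has change from baseline in the visible text.

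**3. How far a raw mean could move with no true change (Part A; all inputs assumed)**

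Let p be the share of subjects without a Week 96 value, S the baseline mean ppFEV1 of those who stay, L that of those who leave, and d = S - L. Suppose that no subject's ppFEV1 changes.

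- Baseline mean of all = (1 - p)S + pL
- Week 96 raw mean = S
- Difference = S - (1 - p)S - pL = p(S - L) = p x d

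| p | Difference for d from -8 to +8 points |
|---|---|
| 0 | 0 |
| 10% | -0.8 to +0.8 |
| 20% | -1.6 to +1.6 |
| 40% | -3.2 to +3.2 |

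A middle case, p = 20% and d = 4, gives 0.20 x 4 = 0.8 points. The mean paired change is 0 throughout, because no true change was assumed. The documents give neither p nor d.

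**4. What raw summaries cannot recover, even with complete data**

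If the SD is s at both visits and the within-subject correlation is r, the SD of change is s x sqrt(2(1 - r)). That is s at r = 0.5 and 0.32s at r = 0.95 (assumed values). Raw tables report s but not r, so the spread of change is unknown from them.

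**The case against.** The strongest objection is that the SAP follows the protocol. Protocol 12.3.3.2 to 12.3.3.5 name change from baseline for laboratory values, ECG, vital signs and pulse oximetry, while 12.3.3.7 asks only for descriptive statistics. This stands as far as it goes: the SAP does not depart from the protocol. But change from baseline is itself descriptive, so adding it fits the protocol.

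Next, the contents list and the body of the public SAP skip from 8.4 to 8.6, and a section 8.5 could hold this analysis. That cannot be excluded, and it limits the finding to the visible text. Section 8.4.8 itself is readable, however, and specifies raw values.

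Third, no harm is shown. Both inputs to the illustration are assumed, no passage links leaving to lung function, and the count of 120 measures scope and not bias. All of this is right. The point is that the planned tables could not tell the two explanations apart, not that a bias has been demonstrated.

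Fourth, mean changes at successive visits also come from different subjects. This is right too. Pairing removes differences in baseline level but does not correct for drop-out that depends on a subject's own decline.

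Finally, by-visit n, disposition counts and the individual listings promised in Protocol 12.3.3 let a reader derive paired change afterwards, and clinical worsening is also captured as adverse events. The gap is therefore in the planned tables and not in the data. With over 400 subjects, reconstruction from listings is a poor substitute for a planned table.

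**Conclusion.** The concern holds for the visible SAP. Of the continuous components compared, spirometry alone has no planned within-subject summary: no change from baseline, no shift and no threshold analysis. This is a weak analysis choice that should be mended. It is neither a protocol departure nor a flaw in the data.

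Its scope is 120 by-visit summaries. Its numerical effect cannot be determined from the documents. The range of -3.2 to +3.2 points rests on assuming up to 40% without a Week 96 value and a stayer-leaver difference of up to 8 points in either direction, and it is 0 if the two groups are alike. The composition argument is made for Part A. The missing distribution of individual change applies to both parts.

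**What to change.** In SAP 8.4.8:

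- Add absolute change from baseline at each visit, using the SAP 8.1 definition, with the number of subjects who have both values. Do this for ppFEV1 first, then the other listed measures, in Parts A and B.
- State that baseline is taken at the switch from VX-659/TEZ/IVA and is not an untreated state.
- Footnote the number of subjects who entered on a drug interruption (Protocol 8.1), because their baseline may follow a gap in treatment.
- If section 8.5 already contains the analysis, a cross-reference from 8.4.8 is enough.

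The cost is SAP wording and extra table columns, with no new data. SAP 3 gives the route: an amendment before database lock, or documentation in the study report if later. Two cautions belong with the tables. Paired change does not repair drop-out that depends on a subject's own decline. Change in litres includes growth in adolescents, so ppFEV1 should be read first.
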